The primary endpoint is to evaluate the **safety and tolerability** of concurrent single/low dose radiotherapy (8 Gy/1fx) in combination with pembrolizumab in relapsed and/or refractory myeloma patients at 3 months (**acute toxicity, primary endpoint**) and at 6 and 12 months (**late toxicity**). The secondary objective is to characterize the effect of radiation in combination with pembrolizumab on systemic response rates using international myeloma working group (IMWG) uniform response criteria for myeloma, to assess baseline changes in PET/CT as a result of combining pembrolizumab and radiotherapy, and to evaluate treatment response at irradiated and un-irradiated sites (i.e. the abscopal effect) using baseline PET/CT. Exploratory analysis would include analyzing Circulating Myeloma Tumor cells and phenotype of T cells as a prognostic and predictive biomarker. Compare blood Myeloma tumor cells with BM tumor cells. We are interested in comparing T cell phenotype after each treatment and using that as a prognostic biomarker. We will also evaluate serum LDH, CRP, ESR, ALC, cytokines and chemokines (such as IL-6, s IL-6R) and other immune related biomarkers, and correlate their expression pre and post treatment and evaluate changes in bone marrow biopsy and peripheral blood for mutational load, mutational signature (whole exome sequencing), transcriptome of the T cells, mutation specific T cells, PD1 and PDL1 expression on MM cells and T cells by flow/IHC, RNA-seq. Other biomarker correlative exploratory analysis (role of exosomes, etc) may also be pursued as ancillary research to this trial;

2. Acute Toxicity and Late Toxicity Assessment:

[figure not shown]
Acute toxicity (i.e. > Grade 2 CTCAE toxicity at **3 months**) associated with radiation therapy at the **radiated site** will be analyzed as the **primary safety endpoint** in this pilot study; Goal would be to see less than 20% > grade 2 toxicity at 3 months within the radiated area.

CTCAE criteria (see Appendix I) will be applied to assess acute toxicity.

Other endpoints that may be analyzed include late toxicity (> Grade 2 CTCAE toxicity at the radiated site at **6 months and 12 months**), systemic response against myeloma burden to localized radiation and pembrolizumab using IMWG uniform criteria, as well as other endpoints (defined in more detail in section 3.0).

3. Trial Schema

Figure 1: Trial Overview

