3. OBJECTIVES, ENDPOINTS & HYPOTHESES

1. Primary Objective, Endpoint, & Hypothesis

Primary Objective

To evaluate the safety of concurrent single/low dose radiotherapy (**8 Gy/1fx**) in combination with Pembrolizumab in relapsed or refractory myeloma patients; **Once 10 patients are enrolled, we will stop trial for 3 months to assess for acute toxicity, and then resume the trial.**

Primary Endpoint

CTCAE > grade 2 toxicity at the specific irradiated **organ site at 3 months** (the Dose Limiting Toxicity);

Primary Hypothesis

The primary hypothesis of this pilot study is that the use of concomitant Pembrolizumab and radiation therapy in multiple myeloma patients will be well tolerated and safe.

Alternative Hypothesis

It is possible that concurrent use of radiotherapy and Pembrolizumab in relapsed/refractory myeloma may increase CTCAE > grade 2 toxicity within the radiated site at 3 months.

2. Secondary Objective(s), Endpoint(s) & Hypothesis (es)

Secondary Objectives

To characterize late toxicity (CTCAE > grade 2 toxicity at **6 and 12 months**) and the effect of radiation in combination with Pembrolizumab on systemic response rates using international myeloma working group (IMWG) uniform response criteria for multiple myeloma at **6 months and 12 months**;

To assess changes in PET/CT as a result of combining Pembrolizumab and radiotherapy at **6 months and 12 months**;

Secondary Endpoints

- a. 1. Number of patients achieving any response (from baseline) per IMWG response criteria at **6 months and 12 months**;
- b. 2. Overall survival time at **6 months and 12 months**;
- c. 3. Overall response based on baseline changes on PET/CT at **6 months and 12 months**;
- d. 4. Difference in pre and post treatment serum immune biomarkers;

Secondary Endpoint Definitions

- a. Response is defined per IMWG criteria, and will be calculated at **6 months and 12 months**;
- b. Overall survival will be defined as time from first treatment on cycle 1, day 1 to the earlier of date of death and/or last follow up at **6 months and 12 months**.
- c. Overall response will be defined using IMWG uniform response criteria.
- d. Several serum biomarkers will be analyzed.

Secondary Hypotheses

The secondary hypothesis is that low dose/single fraction (8Gy/1fx) will synergize with Pembrolizumab for a more effective anti-myeloma response per IMWG, via the radiation induced abscopal response.

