post-treatment follow-up for disease status until disease progression, initiating a non-study cancer treatment, withdrawing consent or becoming lost to follow-up. After documented disease progression each subject will be followed by telephone for overall survival until death, withdrawal of consent, or the end of the study, whichever occurs first.

Discontinuation of Study Therapy after CR

Discontinuation of treatment may be considered for subjects who have attained a confirmed CR that have been treated for at least 24 months with pembrolizumab and had at least two treatments with pembrolizumab beyond the date when the initial CR was declared. Subjects who then experience radiographic disease progression may be eligible for up to one year of additional treatment with pembrolizumab via the Second Course Phase at the discretion of the investigator if no cancer treatment was administered since the last dose of pembrolizumab, the subject meets the safety parameters listed in the Inclusion/Exclusion criteria, and the trial is open. Subjects will resume therapy at the same dose and schedule at the time of initial discontinuation.

Clinical Criteria for Early Trial Termination

Early trial termination will be the result of the criteria specified below:

- 1) Quality or quantity of data recording is inaccurate or incomplete
- 2) Poor adherence to protocol and regulatory requirements
- 3) Incidence or severity of adverse drug reaction in this or other studies indicates a potential health hazard to subjects
- 4) Plans to modify or discontinue the development of the study drug

In the event of Merck decision to no longer supply study drug, ample notification will be provided so that appropriate adjustments to subject treatment can be made.

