9. TRIAL FLOW CHART

9.1 Study Flow Chart (Table 4: Trial Flow Chart)

Procedure	Pre- Treatment (within 28 days of starting)	Cycle 1, Day 1 week 1	Cycle 1, Day 2-3	Cycle 2, Day 22	q 3 WK cycles	q6 WK cycles x 2 yr or until progression	q 3 months (Rad Onc)	q 6 months
Initial Screening	X							
Informed Consent	X							
Inclusion/Exclusion	X							
Prior and Concomitant Medication	X							
Full Physical Examination	X			X				
Review of Systems	X			X		X	X	X
Vital Signs	X	X		X		X	X	X
Weight	X	X		X		X	X	X
ECOG Performance Status	X	X		X		X	X	X
HBcAb, HepC Ab	X							
*Bone Marrow Biopsy	X							X (clinical indication)
PET/CT	X						X	
Adverse effects Assessment	X			X	X (Pembro)	X	X	X
Labs								
Baseline Labs *	X							
Myeloma Labs *, LDH, ESR				X		X		
T3, FT4, TSH	X						X	
Pregnancy Test- urine or ser	X						X	
Urinanalysis	X						X	
uric acid, mg, phos, Coags (PTT,	X							
Correlative Biomarkers								
Serum markers (collect)	X	X (pre-RT)	X (Pre-PD1)	X (pre-PD1)		X (3,6 mo) (Pre-PD1)		
ExtraOssseous/Ossseous Biopsy* (clinical indication)								
Treatment								
*Pembrolizumab 200 mg IV			X	X	X			
RT (8 Gy/1fx)		X						
Survival Analysis								X
IMWG Assessment*	X						X	
CTCAE Toxicity*					X	X		

* EOS = end of study (at progression, or when patient stops being treated on the trial)

* Pembrolizumab 200 mg IV q3wk should be given for at least 2 yr and/or until progression.

* Baseline labs = CBC with Diff, CMP, calcium, Albumin, Serum Protein analysis, Quantitative Immunoglobulin, Serum Immunofixation (SIFE), 24 hr urine total protein, Urine Immune-Fixation, Serum Free Light Chain;

*Bone Marrow Biopsy (with IHC, flow, cytogenetics, FISH);

*Whole Body PET/CT every 3 months (as long as insurance approves);

*Biopsy of Osseous or extra-osseous site (if clinically indicated at baseline);

*Myeloma labs: (CBC with diff, CMP, Calcium, Quantitative Immunoglobulin, M-Protein (serum and Urine), Serum Free Light Chain;

* IMWG Assessment = Done at least during 1st month and every 3 months, or as clinically indicated;

*CTCAE Toxicity at the radiated site once at 3 months, 6 months, and 12 months;

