11. STATISTICAL ANALYSIS PLAN

1. Statistical Analysis Plan Summary

Study Design

The study is a pilot study to look at the safety of concurrent PD-1 inhibitor and SRS for relapsed/refractory myeloma. A total of 24 patients will be enrolled on the trial (20 is the minimum, with an additional 4 patients, to make for any attrition and/or loss to follow-up). 12 patients will be allowed to not have measurable myeloma disease in this trial. Once 10 patients are enrolled, we will stop trial for 3 months to assess for acute toxicity, and then resume the trial. The estimated exact Clopper-Pearson 95% confidence interval for a 20% rate based on 5 responses in 20 patients is (0.087, 0.491), with a precision of 0.185. If we see lower than 20% difference in rate of toxicity at 3 months, the combination will be deemed safe.

A minimum of 20 patients are required to complete full treatments. An additional 20% is allowed for drop out/failure to adhere to required follow-up and treatment recommendations. Thus, 24 patients will be allowed to be enrolled on the trial to make for any attrition and/or loss to follow-up. 12 patients will be allowed to not have measurable myeloma disease.

# of Responses / # of Patients	95% confidence interval
5 / 20	(0.087, 0.491)
6 / 24	(0.098, 0.467)

Populations for analysis

- Enrolled set: All subjects who signed an informed consent.
- Safety set: All subjects who received at least one dose of any study drug.
- Full analysis set: All subjects from the safety set who have the required follow-up and treatment adherence to evaluate response and safety over time.

2. Statistical Analyses

1. Response

IMWG criteria will be used to assess response. Proportion of patients achieving stable

disease or better will be reported at **6 months** and **12 months**; Response rates will be reported along with 95% confidence intervals will be estimated using the Clopper-Pearson method.

2. Safety

Proportion of acute (at **3 months**) and late toxicity (**6 and 12 months**) will be reported, and 95% confidence intervals will be estimated using the Clopper-Pearson method.

3. Overall Survival

For overall survival, death from any cause will be defined as the event. Patients will be censored at time of last follow-up. OS will be estimated using the Kaplan-Meier product-limit method. Overall survival will be analyzed at **6 months, and 12 months**.

4. Biological variables

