13.0 DATA AND SAFETY MONITORING PLAN

The Data and Safety Monitoring Committee (DSMC) of the Winship Cancer Institute will provide oversight for the conduct of this study. The DSMC functions independently within Winship Cancer Institute to conduct internal monitoring functions to ensure that research being conducted by Winship Cancer Institute Investigators produces high-quality scientific data in a manner consistent with good clinical practice (GCP) and appropriate regulations that govern clinical research. Depending on the risk level of the protocol, the DSMC review may occur every 6 months or annually. For studies deemed High Risk, initial study monitoring will occur within 6 months from the date of the first subject accrued, with 2 of the first 5 subjects being reviewed. For studies deemed Moderate Risk, initial study monitoring will occur within 1 year from the date of the first subject accrued, with 2 of the first 5 subjects being reviewed. Subsequent monitoring will occur in routine intervals per the [Winship Data and Safety Monitoring Plan \(DSMP\)](#).

The DSMC will review pertinent aspects of the study to assess subject safety, compliance with the protocol, data collection, and risk-benefit ratio. Specifically, the Winship Cancer Institute Internal Monitors assigned to the DSMC may verify informed consent, eligibility, data entry, accuracy and availability of source documents, AEs/SAEs, and essential regulatory documents. Following the monitoring review, monitors will provide a preliminary report of monitoring findings to the PI and other pertinent individuals involved in the conduct of the study. The PI is required to address and respond to all the deficiencies noted in the preliminary report. Prior to the completion of the final summary report, monitors will discuss the preliminary report responses with the PI and other team members (when appropriate). A final monitoring summary report will then be prepared by the monitor. Final DSMC review will include the final monitoring summary report with corresponding PI response, submitted CAPA (when applicable), PI Summary statement, and available aggregate toxicity and safety data.

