The DSMC will render a recommendation and rating based on the overall trial conduct. The PI is responsible for ensuring that instances of egregious data insufficiencies are reported to the IRB. Continuing Review submissions will include the DSMC recommendation letter. Should any revisions be made to the protocol-specific monitoring plan after initial DSMC approval, the PI will be responsible for notifying the DSMC of such changes. The Committee reserves the right to conduct additional audits if necessary.

14.1. Data Collection:

Data that will be captured in OnCore for the following procedures

- Inclusion/Exclusion Criteria
- Vital Signs
- Weight
- Karnofsky Performance Status (KPS) & ECOG
- HBcAb, HepC Ab
- PET/CT Diagnostic Imaging [RECIST]
- Adverse Events Assessment
- CBC with differential

- CMP
- T3, FT4, TSH
- Pregnancy Test – urine or serum b-HCG
- Urinalysis
- Uric Acid, MG, Phos, Coags (PTT, PT, INR) - [seconds]
- Serum Biomarkers
- Osseous, extra-osseous, bone marrow biopsy (if done, and what date it was done)

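### The safety pause after patient 10 ends in unconditional resumption: no count of dose-limiting toxicities and no named decision-maker governs whether patients 11 to 24 are treated

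*Combined protocol and SAP*

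**What the plan says.** Section 3 (Primary Objective) and Section 11 (Study Design) give the same instruction: "Once 10 patients are enrolled, we will stop trial for 3 months to assess for acute toxicity, and then resume the trial".

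The event to be assessed is well defined. Section 3 names it the Dose Limiting Toxicity: "CTCAE > grade 2 toxicity at the specific irradiated" organ site at 3 months. The flow chart in Section 9.1 schedules the assessment: "CTCAE Toxicity at the radiated site once at 3 months, 6 months, and 12 months".

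A numerical standard appears twice, both times for the trial as a whole. Section 2 (Acute Toxicity and Late Toxicity Assessment) says: "Goal would be to see less than 20% > grade 2 toxicity at 3 months within the radiated area". Section 11 says: "If we see lower than 20% difference in rate of toxicity at 3 months, the combination will be deemed safe". There is no comparator, so I read the second sentence as an observed rate below 20%.

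The list of clinical criteria for early trial termination in Section 7 has one toxicity item, item 3: "Incidence or severity of adverse drug reaction in this or other studies indicates a potential health hazard to subjects". It carries no number and does not name radiotherapy.

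**The concern.** Safety is the primary objective, and the pause is the only point at which the plan stops accrual to look at the primary endpoint. Everything a decision rule needs is already in the protocol: a defined event, a scheduled assessment, a target rate and an independent committee. They are not connected. The sentence that creates the pause also ends it, whatever was seen.

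At stake is whether 14 more patients receive the combination after a poor result in the first 10. An investigator who follows the text exactly has no written reason to wait. One who does wait must decide after seeing the data what counts as too many.

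**Working it through.** **The plan's own figures.** No figure is given for the pause. The nearest are the two Clopper-Pearson intervals in Section 11. I obtain (0.0866, 0.4910) for 5/20 and (0.0977, 0.4671) for 6/24, which match the stated values. They describe the final estimate and do not inform the decision at patient 10.

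**Inputs.**
- 10 patients at the pause; 24 in total, with a planned minimum of 20 (Section 11).
- Goal: under 20% (Sections 2 and 11).
- 24 patients over two years, or about 1 per month (Section 10, Enrollment and Treatment Period).
- True rate *p* of the primary toxicity: **assumed**, because the documents give no rate for an irradiated site. The nearest figures are in Section 4.4, for grade 3-4 toxicity of any kind with pembrolizumab in melanoma: 12-13% overall, and 4-9% on 3-weekly schedules such as the one used here.

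**What the text implies.** With no count, the probability of a count-based hold is zero at every *p*. Suppose 5 of 10 are affected (95% CI 0.187 to 0.813): the text still says to resume. The next 14 patients would then be expected to have 14 × 0.30 = 4.2 events at a true 30%, or 14 × 0.40 = 5.6 at 40%.

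**Why 3 of 10 is informative.** Staying under 20% allows at most 4 affected of 24 (16.7%; 5/24 = 20.8%) or 3 of 20 (15%; 4/20 is exactly 20%).
- After 3 of 10, a trial of 24 can afford at most 1 of the next 14. The chance is (1−*p*)^14 + 14*p*(1−*p*)^13 = 59%, 20% and 5% at true rates of 10%, 20% and 30%.
- With only 20 evaluable it can afford none of the next 10: 0.9^10 = 35% at a true 10%.

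**A rule that holds at 3 or more of 10.** P(hold) = 1 − Σ(k=0..2) C(10,k) *p*^k (1−*p*)^(10−k). For example, at 30%: 1 − (0.0282 + 0.1211 + 0.2335) = 0.617.

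| Assumed true rate | 4% | 9% | 10% | 15% | 18% | 20% | 30% | 40% |
|---|---|---|---|---|---|---|---|---|
| P(hold) | 0.6% | 5.4% | 7% | 18% | 26% | 32% | 62% | 83% |

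**Other cuts.** Holding at 2 of 10 would stop 26% of trials at a true 10% and 46% at 15%. Holding at 4 of 10 would stop only 35% at a true 30%.

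**Mean enrolment at first review** (24 if never held) is 10 × P(hold) + 24 × (1 − P(hold)).
- At 30%: 10 × 0.617 + 24 × 0.383 = 15.4.
- At 40%: 10 × 0.833 + 24 × 0.167 = 12.3.

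**Adding a review at the 5th affected patient in total.** This was simulated at 1 patient per month, with events known at 3 months. The two rules together trigger before full enrolment in about 10%, 27%, 40%, 49%, 83% and 97% of trials at true rates of 10%, 15%, 18%, 20%, 30% and 40%. The timing conventions of the simulation can move these by a few points. Mean enrolment falls only from 15.4 to about 14.4 at 30%, and from 12.3 to about 11.7 at 40%.

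**The case against.** The strongest reply is that the trial is not unguarded, and much of this stands.
- Serious adverse events reach the sponsor within 24 hours whatever their cause, and the sponsor monitors aggregate safety data (Section 10). Many grade 3 events will qualify as serious.
- IND safety reports and the unanticipated-problem route bring in the FDA and the IRB (Section 10, Sponsor Responsibility for Reporting Adverse Events).
- Section 8 requires an immediate alert to the study coordinator for novel or unexpected grade 3 or higher toxicity suspected to come from the combination.
- The monitoring committee assesses risk-benefit and issues a recommendation. Section 13.0 says "Depending on the risk level of the protocol, the DSMC review may occur every 6 months or annually" and adds "The Committee reserves the right to conduct additional audits if necessary".
- Item 3 of the termination list can be invoked on judgement at any time.

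A reader might therefore infer the opposite extreme, that the protocol has no means of stopping for toxicity. The documents do not support that; the gap is the missing link between the count and the hold. The Winship monitoring plan cited in Section 13.0 was not supplied either, so a trigger held there cannot be excluded.

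A reader might also infer that radiotherapy toxicity could never stop the trial, because item 3 speaks only of a drug reaction. That is too strong. Section 10 counts worsening associated with radiotherapy as an adverse event. Pembrolizumab follows radiation by a day or two, and the attribution scale in Section 8 has no unrelated category. An irradiated-site event wholly outside item 3 is a narrow case.

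A third tempting reading is that the lack of a count in patients 11 to 24 is as serious as the open pause. The arithmetic does not bear that out: a later trigger saves about one patient or fewer on average.

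Finally, the 30-40% rates that show the rule at its best have no support in the documents, and any cut is a choice. Both points are fair. At 4-9% the proposed rule would almost never act.

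**Conclusion.** The point holds for the pause. As written, resumption after patient 10 is unconditional, with no count and no decision-maker, and the discretionary cover elsewhere does not tie the primary toxicity to a hold. This should be corrected, though it does not show that the trial is unsafe as run.

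The size depends on a true rate that nobody can supply from the documents. A hold at 3 of 10 would catch 62% of trials at 30% and 83% at 40%, where the present text calls for none. The figures also assume 10 evaluable patients with independent outcomes and a common rate. Confidence is medium, because the institutional monitoring plan was not available. The wording of termination item 3 is a minor matter, and a later count-based review is optional.

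**What to change.** **Main change, in Sections 3 and 11.** Replace the automatic restart with: *resume if at most 2 of the first 10 patients evaluable at 3 months have the primary toxicity; if 3 or more do, accrual stays on hold until the Winship DSMC reviews and recommends resume, modify or stop.* Report the hold probabilities tabulated above beside it, and say how a first-10 patient who cannot be assessed at 3 months is handled.

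**Wording, in Section 7, termination item 3.** Refer to an *adverse reaction to pembrolizumab, radiotherapy or their combination*.

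**Optional.** Add a further DSMC review at the 5th affected patient in total. If only 20 patients prove evaluable, the 4th event already misses the under-20% goal, so the 5th would come late.

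**Cost.** A short amendment that uses the existing pause, committee and data. The main rule sends 7%, 18% and 26% of trials to review at true rates of 10%, 15% and 18%, all of which meet the goal; with the optional review this becomes about 10%, 27% and 40% before full enrolment. Each is a review, not a termination. The rule also lets 2 of 10 pass, although 20% is not itself under the goal; the stricter cut would hold too many acceptable trials.

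### The sample-size sentence calls 5/20 a 20% rate and pairs it with a precision that matches 6/24, so no interval is shown at the plan's own 20% toxicity threshold

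*Combined protocol and SAP*

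**What the plan says.** Section 11, Study Design, sets the method with "The estimated exact Clopper-Pearson 95% confidence interval" and then gives the result "for a 20% rate based on 5 responses in 20 patients is (0.087, 0.491), with a precision of 0.185". A two-row table follows: 5/20 with limits (0.087, 0.491) and 6/24 with limits (0.098, 0.467). The column header speaks of responses and does not say whether these are toxicities or IMWG responses. Precision is not defined.

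The decision rule comes directly after the interval: "If we see lower than 20% difference in rate of toxicity at 3 months, the combination will be deemed safe". Section 2, under Acute Toxicity and Late Toxicity Assessment, states the same threshold as a target: "Goal would be to see less than 20% > grade 2 toxicity at 3 months within the radiated area".

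On numbers, Section 11 says "A minimum of 20 patients are required to complete full treatments" and "A total of 24 patients will be enrolled on the trial". The difference of 4 is a 20% allowance for attrition. Apart from that allowance, the interval sentence and its table are the only quantitative support for the trial's size.

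**The concern.** Three things in the sentence and table do not fit together. The count 5/20 is not 20%. The stated precision is not the half-width of the interval printed beside it. And both table rows are the same rate, 25%, which is above the threshold used to call the combination safe.

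A reader who wants to know how well 20 patients can pin down a toxicity rate of 20% is given the interval for 25% and a precision that fits 24 patients. Nothing shows the interval at 20%, or at any count that would pass the rule. This is the stated basis for the 20-patient minimum and it stands next to the primary safety criterion, so the error is likely to be carried into any report that quotes the design.

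**Working it through.** **Inputs.** From Section 11: counts 5/20 and 6/24, the exact Clopper-Pearson method at two-sided 95%, printed limits (0.087, 0.491) and (0.098, 0.467), stated precision 0.185. From Sections 2 and 11: threshold 20%.

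**Formula.** For x events in n patients, the lower limit is the 2.5% quantile of Beta(x, n − x + 1) and the upper limit is the 97.5% quantile of Beta(x + 1, n − x). Precision is taken as the half-width, (upper − lower)/2.

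**Step 1: reproduce the printed intervals.** 5/20 gives (0.0866, 0.4910) and 6/24 gives (0.0977, 0.4671). Both printed intervals are right.

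**Step 2: the rate label.** 5/20 = 0.25. A 20% rate in 20 patients is 0.20 × 20 = 4 events. The sentence and the table agree on the count 5/20 and on its limits, so the wrong item is the 20% label.

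**Step 3: the precision.** From the printed limits:

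- 5/20: (0.491 − 0.087)/2 = 0.202
- 6/24: (0.467 − 0.098)/2 = 0.1845 (0.1847 from unrounded limits)

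The stated 0.185 therefore matches 6/24 and not 5/20. Because precision is undefined, other readings were tried:

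| Reading, for 5/20 | Value |
|---|---|
| Distance from 0.25 to the exact lower limit | 0.163 |
| Distance from 0.25 to the exact upper limit | 0.241 |
| Normal approximation, 1.96 × √(0.25 × 0.75/20) | 0.190 |
| Wilson half-width | 0.178 |
| Agresti-Coull half-width | 0.182 |
| Jeffreys half-width | 0.181 |
| 90% Clopper-Pearson half-width | 0.176 |

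None rounds to 0.185. A true 20% in 20 patients does not give it either: the exact half-width for 4/20 is 0.190, and the normal approximation, 1.96 × √(0.20 × 0.80/20), is 0.175.

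**Step 4: intervals around the threshold.**

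| Events/patients | Rate | Exact 95% interval | Half-width | In the plan's table? |
|---|---|---|---|---|
| 3/20 | 15.0% | (0.032, 0.379) | 0.173 | no |
| 4/20 | 20.0% | (0.057, 0.437) | 0.190 | no |
| 5/20 | 25.0% | (0.087, 0.491) | 0.202 | yes |
| 4/24 | 16.7% | (0.047, 0.374) | 0.163 | no |
| 5/24 | 20.8% | (0.071, 0.422) | 0.175 | no |
| 6/24 | 25.0% | (0.098, 0.467) | 0.185 | yes |

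No count in 24 patients gives exactly 20%, since 0.20 × 24 = 4.8. If the rule is read as an observed rate below 20%, the largest passing counts are 3/20 and 4/24. Neither is tabulated, and their upper limits are 0.379 and 0.374.

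**The case against.** The best defence is that little follows from the error. Both printed intervals are correct, and the count 5/20 stands beside the wrong label, so a careful reader can see 25%. Section 11 (Safety) commits to Clopper-Pearson intervals for the observed toxicity proportions, so the final report will be right whatever this sentence says. No precision target is stated from which 20 was derived, so correcting the figures cannot move the sample size. All of this is true, and it limits the consequence. It does not repair a justification that contradicts itself.

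A second argument is that the rule refers to an observed rate and not to a confidence limit, so no interval at 20% is needed to apply it. That also stands. But the sentence says it is giving the interval for 20%, and it does not.

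Third, the counts may have been meant as IMWG responses, for which Section 11 also plans exact intervals. The document does not settle this. On either reading 5/20 is 25% and 0.185 is not its half-width. The point does bear on how the table should be re-headed, and only the sponsor can say which endpoint was meant.

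Finally, tracing 0.185 to 6/24 is an inference from a numerical match. What is certain is that 0.185 is the exact half-width of neither 5/20 nor 4/20.

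**Conclusion.** The error is confirmed. The rate is stated as 20% where the count gives 25%, a difference of 5 percentage points. The half-width is stated as 0.185 where the quoted interval gives 0.202 (0.017, or 9%, wider) and a true 20% in 20 patients gives 0.190 (0.005 wider). For an observed 20% the interval should read (0.057, 0.437), not (0.087, 0.491). No interval is given at the threshold or at any count below it.

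This rests on two readings. Precision is taken to mean half-width; none of the alternatives tried rescues the figure. The threshold is taken as an absolute observed rate: the rule in Section 11 speaks of a difference without naming a comparator, but the target in Section 2 supports the absolute reading. The label and precision errors hold without the second assumption.

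The statement is wrong as written in the only justification for the 20-patient minimum, next to the primary safety rule, and should be corrected. It does not affect enrollment, the decision rule or the analysis method.

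**What to change.** Replace the sentence with one that states the count, rate, interval and half-width consistently, for example: *For an observed toxicity rate of 20% (4/20), the exact Clopper-Pearson 95% confidence interval is (0.057, 0.437), half-width 0.190.*

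Head the table as the number with > grade 2 toxicity over the number of patients, add a column for the percentage, and show the rows on either side of the threshold:

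- 3/20 (15%): (0.032, 0.379), half-width 0.173
- 4/20 (20%): (0.057, 0.437), half-width 0.190
- 4/24 (16.7%): (0.047, 0.374), half-width 0.163
- 5/24 (20.8%): (0.071, 0.422), half-width 0.175

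Note under the table that no count in 24 patients equals 20%. If the table is meant for IMWG response, or for both endpoints, the header should say so.

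If the sponsor prefers to keep the present rows, the minimum correction is to label both 25%, give half-widths of 0.202 (5/20) and 0.185 (6/24), and remove the 20% label from 5/20.

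The cost is one sentence and one small table in Section 11. Planned enrollment stays at 24.
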